#### **Abbreviations**

AE adverse event

BCDVA best corrected distance visual acuity

BCVA best corrected visual acuity
CFR Code of Federal Regulation
CMH Cochran-Mantel Haenszel
eCRF Electronic case report form

CI Confidence interval CRF Case report form

ETDRS Early Treatment Diabetic Retinopathy Study

FDA Food and Drug Administration

HIPAA Health Information Portability and Accountability Act

IB Investigator's Brochure ICF informed consent form

ICH International Conference on Harmonization

IRB institutional review board

ITT intent-to-treat

MedDRA medical dictionary for regulatory activities

NEI-VFQ National Eye Institute Visual Function Questionnaire

mg Milligram

NK Neurotrophic Keratitis

μL microliter
mL Milliliter
mm millimeter

PED Persistent Epithelial Defect

SAE serious adverse event SAP Statistical Analysis Plan

SD Standard deviation STS Schirmer's Test Score

TEAE treatment-emergent adverse event

US United States

#### 2 Introduction

This statistical analysis plan (SAP), which is based on the final protocol (Amendment 6) of the study protocol dated June 15, 2022, defines the methods, and analyses that Oyster Point Pharma, Inc. (henceforth, Oyster Point) plans to use to analyze the data from Protocol OPP-102. This SAP complies with guidance promulgated by the International Conference on Harmonization (ICH) and the US Food and Drug Administration (FDA). If the protocol is subsequently amended, this SAP may be amended as well. Should the SAP and the protocolbe inconsistent with respect to the planned analyses, the language of the SAP prevails.

#### 3 Study objective

The objective of this study is to evaluate the safety and effectiveness of OC-01 (varenicline)nasal spray as compared to placebo for mean change from baseline in corneal fluorescein staining in subjects with Stage 1 (corneal epithelial hyperplasia/punctate keratopathy) NK in one or both eyes.

#### 4 Study Design

This is a Phase 2, multicenter, randomized, controlled, double- masked study designed to evaluate the safety and efficacy of OC-01 (varenicline) nasal spray in subjects with NK. Approximately 100 subjects at least 18 years of age with a physicians' diagnosis of Stage 1 NK, as defined by the Mackie Criteria and meeting all other study eligibility criteria will berandomized 1:1 and will receive OC-01 (varenicline)/ nasal spray or placebo nasal spray for8 weeks (56 days) three times daily (TID).

The two treatments are:

- Placebo (vehicle) [control]
- OC-01 (varenicline) Nasal Spray, 1.2 mg/mL

Subjects who terminate early during the application period will be asked to complete safety and/or efficacy assessments (if the participants agree) prior to study exit. Participants who are terminated early from the study will not be replaced.

Appendix 1 describes the detailed study visits, measurements, and dosing information.

## 5 Primary, Secondary and Exploratory Endpoints

#### 5.1 Primary Efficacy Endpoint

The primary endpoint will be the mean change from baseline in corneal fluorescein staining at Week 8.

#### 5.2 Secondary Efficacy Endpoint

The secondary efficacy endpoint is the mean change from baseline in ETDRS visual acuity at Week 8.

#### 5.3 Exploratory Efficacy Endpoint

- Percent of subjects who achieve ≥ 3 lines (15 letters) of improvement in ETDRS visual acuity at Week 8.
- Percent of subjects who achieve complete resolution of corneal staining will be the exploratory endpoint. Complete resolution of corneal staining will be the exploratory endpoint is defined as complete resolution of corneal staining (0 mm lesion and no residual staining) in subjects with Stage 1 NK at Week 8.
- Percentage (%) of subjects that progress to Stage 2 Persistent Epithelial Defect (PED) NKat Week 8.
- Improvement in corneal sensitivity at Week 8
- Mean change from baseline in corneal fluorescein staining in subjects with Stage 2 NK at Week 8.
- Schirmer's score with topical anesthesia
- Pain visual analog scale (VAS)
- Slit lamp biomicroscopy
- NEI-VFQ-25 Survey

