# 5.4. Exclusion Criteria

#### Subjects must not:

- 1. Have Stage 2 or Stage 3 NK affecting one or both eyes.
- 2. Have ocular graft versus host disease or Stevens-Johnson syndrome.
- 3. Have any active ocular infection (COVID-19 conjunctivitis, bacterial, viral, fungal, or protozoal) or active ocular inflammation not related to NK in the affected eye.

- 6. Be currently receiving autologous serum tears, amniotic membrane, cenegermin, Fresh Frozen plasma or cord blood derived tears.
- 7. Have severe blepharitis and/or severe meibomian gland disease in the study eye.

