# 5.5. Withdrawal Criteria

If at any time during the study the Investigator determines that a subject's safety has been compromised, the subject may be withdrawn from treatment, but will be followed for safety for the duration of the study, unless they refuse to attend follow-up visits.

Additionally, if a subject should progress to Stage 2 NK while receiving the study drug, the subject should remain in the study and receive treatment. If a subject should progress to Stage 3 NK while receiving study treatment, the subject may be withdrawn from treatment at the discretion of the Investigator. The subject will continue to be followed for safety unless the subject refuses to attend the follow-up visits.

A subject may withdraw consent from the study at any time.

The Sponsor and/or the Investigator may discontinue any subject from study treatment for noncompliance or for any valid medical reason during the study (see Section 8.6.2).

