## **Corneal Fluorescein Staining**

The examiner should instill 5  $\mu$ L of 2% preservative-free sodium fluorescein solution into the inferior conjunctival cul-de-sac of each eye. Alternatively, corneal staining can be assessed using 1.0 mg sodium fluorescein strips. After moistening the tip of the strip with sterile buffered saline, the excess is shaken into a waste bin with a sharp flick. The lower lid is then

pulled down and the flat end of the tip should be gently applied to the inferior tarsal conjunctiva with the intent of not inducing reflex tearing and instilling a very small volume of dye.

[figure not shown]
The subject will be instructed to blink naturally several times without forced closure of the eyelid to distribute the fluorescein. To achieve maximum fluorescence, the examiner should wait at least two minutes after instillation before evaluating corneal fluorescein staining. A Wratten #12 yellow filter will be used to enhance the ability to grade fluorescein staining. The staining will be graded with the modified Oxford Grading Scale.

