#### **Modified Oxford Grading Scale**

The examiner compares the overall appearance of the patient's corneal staining with the reference figure (below) and selects the appropriate grade that best represents the state of corneal staining.

For subjects that progress to Stage 2, graders will assess the following:

- Lesion size
- Is any residual staining present (Yes/No)?
- If residual staining is present, is the staining persistent (Yes/No)?

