# The Grade 0 corresponds to none staining dots

## **Corneal Sensitivity**

#### **Cochet-Bonnet Aesthesiometer**

Corneal sensation is measured in the affected eye of the patient at all applicable visits using a Cochet Bonnet aesthesiometer. The measurements taken from the affected eye are as follows:

Sensitivity in each of the 4 quadrants of the cornea:

- Superior nasal (cm)
- Inferior nasal (cm)
- Superior temporal (cm)
- Inferior temporal (cm)

Steps for using the handheld aesthesiometer:

Note: Cochet Bonnet aesthesiometer measurements MUST be performed prior to administration of Topical Anesthesia

- Sterilize the filament, by wiping only the tip with an alcohol pad, do not wipe the entire length of the filament or pull on the filament.
- Extend the filament to full length of 6 cm.
- Perform sensitivity in each of the 4 quadrants of the cornea:
- Superior nasal (cm)
- Inferior nasal (cm)
- Superior temporal (cm)
- Inferior temporal (cm)
- Retract the filament incrementally in 0.5 cm steps until the patient can feel its contact.
- Record the length (NOTE: The shorter the length indicates decreased sensation.)
- Compare the fellow eye cornea.
- Repeat steps 1-4 in each quadrant: superior nasal, inferior nasal, superior temporal, and inferior nasal.
- Sterilize the filament tip by gently wiping with an alcohol pad and retract back into the device to protect it from damage.

For Stage 1 subjects, corneal sensitivity is defined as the mean of the 4 quadrants (four measurements)

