# 9.11.4Corneal Sensitivity

Corneal sensitivity will be performed at Screening (Visit 1, prior to Schirmer's Test), Week 4(Visit 4), and Week 8 (Visit 6).

Corneal sensation is measured in the affected eye of the patient at all applicable visits using a Cochet Bonnet aesthesiometer. The measurements taken from the affected eye are as follows: Sensitivity in each of the 4 quadrants of the cornea:

- Superior nasal (cm)
- Inferior nasal (cm)
- Superior temporal (cm)

• Inferior temporal (cm)

Steps for using the handheld aesthesiometer:

Note: Cochet Bonnet aesthesiometer measurements MUST be performed prior toadministration of Topical Anesthesia.

- Sterilize the filament.
- Extend the filament to full length of 6 cm.
- Perform sensitivity in each of the 4 quadrants of the cornea:
- Superior nasal (cm)
- Inferior nasal (cm)
- Superior temporal (cm)
- Inferior temporal (cm)
- Retract the filament incrementally in 0.5 cm steps until the patient can feel its contact.
- Record the length (NOTE: The shorter the length indicates decreased sensation.)
- Compare the fellow eye cornea.
- Repeat steps 1-4 in each quadrant: superior, temporal, inferior, nasal.
- Sterilize the filament and retract back into the device to protect it from damage.

For Stage 1 subjects, corneal sensitivity is defined as the mean of the 4 quadrants (four measurements).

The superior nasal, inferior nasal, superior nasal, inferior temporal, sensitivity within the area of PED, and mean score will be calculated at each visit. Corneal sensitivity results will be summarized for each treatment group for the study and fellow eyes by visit using discrete summary statistics.

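### Do the Stage 2 staining endpoint and the lesion-based definition of complete resolution in SAP 5.3 need to be rewritten?

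*SAP*

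**What the plan says.** The protocol enrols Stage 1 disease only. Section 5.4 bars anyone who would "Have Stage 2 or Stage 3 NK affecting one or both eyes". Section 5.5 then provides that "if a subject should progress to Stage 2 NK while receiving the study drug, the subject should remain in the study", so Stage 2 disease can appear during follow-up.

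SAP 5.3 and the SAP synopsis list among the exploratory endpoints "Mean change from baseline in corneal fluorescein staining in subjects with Stage 2 NK at Week 8". The same list has the percentage of subjects who progress to Stage 2, and complete resolution, defined as "complete resolution of corneal staining (0 mm lesion and no residual staining) in subjects with Stage 1 NK at Week 8".

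Protocol Appendix 2 describes how staining is scored: "The staining will be graded with the modified Oxford Grading Scale". Its bottom category is explained by the note "The Grade 0 corresponds to none staining dots". Under the heading for that scale it adds: "For subjects that progress to Stage 2, graders will assess the following", followed by lesion size and yes/no questions on residual staining.

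SAP 9.11.4 plans that "sensitivity within the area of PED, and mean score will be calculated at each visit", whereas Appendix 2 measures sensitivity in four quadrants. Protocol 10.5.5 names Mackie stage as a term in the primary model; SAP 14.1 does not.

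**The concern.** Three things look wrong.

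First, if no one may enter with Stage 2 disease, a Stage 2 group at Week 8 consists of people whose disease worsened after randomisation. The drug may influence who worsens. An arm comparison within that group would set side by side people selected by an outcome, without the protection of randomisation and with few subjects.

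Second, complete resolution in Stage 1 subjects is worded with a lesion measured in millimetres. The visible protocol asks for lesion size only in progressors, and an Oxford grade has no millimetre component. Two programmers might code the endpoint differently or use different denominators.

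Third, Appendix 2 does not say in so many words that the lesion items come on top of the Oxford grade. If they took its place, progressors would have no Week 8 score for the primary endpoint. The sensitivity item for the defect area and the Mackie model term raise the same suspicion, that parts of the plan were written for a wider range of stages than the trial enrols.

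**Working it through.** The plan states no figure for these endpoints, so there is none to reproduce. The check compares sections, with arithmetic on assumed progression rates to show scale. The only design input is about 50 subjects per arm (protocol 5.1).

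**1. Is a test planned in the Stage 2 group?** SAP 9.11.5 describes the staining score by visit, treatment and eye with summary statistics. The legible part of SAP 14 attaches the 5% level to the primary and secondary endpoints. SAP 14.3 has a heading for exploratory endpoints but no legible body. No test of this group is visible.

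**2. How large would the group be?** Expected number per arm = 50 × progression rate. At 5% this is 2.5; at 10%, 5; at 20%, 10. At 5%, the chance that an arm has no progressor is 0.95^50 = 0.08, and the chance of fewer than two is 0.28.

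**3. How precise would a comparison be?** The 95% half-width in SD units is t(0.975, a+b−2) × √(1/a + 1/b).

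| Progressors (a, b) | Half-width (SD) |
|---|---|
| 3, 3 | 2.776 × √(1/3 + 1/3) = 2.27 |
| 5, 5 | 2.306 × √(1/5 + 1/5) = 1.46 |
| 2, 8 | 2.306 × √(1/2 + 1/8) = 1.82 |
| 10, 10 | 2.101 × √(1/10 + 1/10) = 0.94 |
| 50, 50 (all subjects) | 1.984 × √(1/50 + 1/50) = 0.40 |

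**4. How far could selection distort it?** Take a latent tendency to progress and a staining change that are bivariate normal with correlation ρ. The drug shifts both by d = 0.5 SD, and 20% of placebo subjects progress. The cut is c = 0.842, and 9.0% progress on active. The expected arm difference among progressors is −d + ρ × [φ(c+d)/(1−Φ(c+d)) − φ(c)/(1−Φ(c))]. The bracket is 1.805 − 1.400 = 0.405.

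- ρ = 0: −0.50
- ρ = 0.5: −0.50 + 0.203 = −0.30
- ρ = 0.8: −0.50 + 0.324 = −0.18

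A simulation with d of 0.25 or 0.50, placebo progression of 10% to 30% and ρ of 0.5 or 0.8 left 33% to 62% of the true benefit visible among progressors.

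**5. Can complete resolution be computed?** In the Mackie table of Appendix 2, a persistent epithelial defect marks Stage II. An eye that never progressed has no such lesion, so the 0 mm condition is met by its stage, and absence of residual staining is Oxford grade 0. For a progressor, lesion size and residual staining are recorded directly. Both groups can be classified.

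**6. Do progressors keep an Oxford grade?** Appendix 2 (Corneal Fluorescein Staining) and SAP 9.11.5 apply the grade with no exception by stage. The progressor items sit under the Oxford heading. A change from baseline in staining for Stage 2 subjects also presupposes a follow-up staining score. Reading the items as a replacement is strained.

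**7. Does the Mackie term alter the primary analysis?** At entry everyone is Stage 1, so the term is constant and cannot be estimated apart from the intercept. SAP 14.1 leaves it out. Protocol 10.5 and SAP 2 both say the SAP governs where the two differ. SAP 5.1 and 14.1 state the primary endpoint with no restriction by Week 8 stage.

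**The case for a change.** The strongest reply is that a definition should stand on its own. SAP 5.3 calls the Stage 2 item an efficacy endpoint and does not call it descriptive. A reader handed a table by arm will compare the arms, and step 4 shows that the comparison can mislead. Naming grade 0 and a denominator would also cost only a few words.

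The facts behind this stand. The Stage 2 group can arise only by progression, barring an ineligible enrolment, and a lesion in millimetres is not an Oxford term. The denominator is not spelled out in the visible text. With 15 of 50 resolved in each arm and 2 versus 8 progressors, keeping everyone gives 15/50 − 15/50 = 0. Dropping progressors gives 15/48 − 15/42 = 31.2% − 35.7% = −4.5 points.

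That gap arises only if Stage 1 is read as the stage at Week 8. The objective and the hypothesis (SAP 3 and 8) name Stage 1 as the population and do not tie it to a visit, so stage at entry is the natural reading. Read the same way, the Stage 2 item describes an empty group and is a leftover. Read as current stage, it is a small summary of progressors. Neither reading touches an inferential result in the visible plan.

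The tidying is also less simple than it looks. Counting every progressor as unresolved would fail a subject who progressed and then healed to grade 0 by Week 8. That is a new rule, open to debate, and not a clarification.

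**Conclusion.** No change is needed. The Stage 2 item and the defect-area sensitivity measure are loose wording or leftovers. The complete-resolution definition leaves a gap that an analyst would fill with Oxford grade 0. The Mackie term is already overridden by the SAP. The SAP rests on a June 2022 amendment while the supplied protocol carries a November 2022 footer, so some of the mismatch may be a difference of versions.

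The visible primary and secondary analyses are unaffected. What remains is an exploratory summary on perhaps a handful of subjects, with an interval of roughly ±0.9 to ±2.3 SD for 20 down to 6 progressors split equally. All progression rates, effect sizes and correlations used here are assumptions; only the 50 per arm comes from the protocol.

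The conclusion rests on the legible text. If SAP 14.3 did plan a formal arm comparison among progressors, the selection problem in step 4 would be real, though still confined to an exploratory result.

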# **6** Sample Size Determination and Power Calculation

#### 7 Randomization

Subjects will be randomized 1:1 to receive as a 50 microliter (µL) spray in each nostril:

- OC-01 (varenicline) nasal spray, 1.2 mg/mL
- Placebo (vehicle control) nasal spray

The randomization will be stratified by pre-procedure (Baseline) non-anesthetized Schirmer's score  $(\le 5, \ge 5)$  measured at thescreening/randomization visit.

#### 8 Statistical Hypothesis Testing

Let  $\mu_h$ , and  $\mu_p$  denote the mean change in corneal fluorescein staining from baseline to Week 8 (1.2 mg/mL OC-01 and placebo, respectively) in subjects with Stage 1 NK.

 $H_0$ :  $\mu_h$ - $\mu_p = 0$ 

VS.

 $H_1: \mu_h - \mu_p \neq 0$ 

#### 9 Statistical Analysis

#### 9.1 General Consideration

Quantitative variables will be summarized using the number of subjects (n), mean, SD, median, 25th and 75th percentiles, and minimum and maximum. Qualitative variables will besummarized using counts and percentages.

[figure not shown]
All summaries will be presented by treatment group. Summaries will be provided fordemographics, medical history, concomitant medications, and subject disposition.

For the summaries, medical history, concomitant medications, and AEs will be coded to MedDRA version 24 and World Health Organization Drug dictionaries March 2021 version,as appropriate.

Baseline measures are defined as the last measure prior to the initiation of study treatment, usually at Visit 1 screening.

All summaries for safety data and efficacy data will be presented by treatment group. For thebaseline characteristics, all summaries will be presented by treatment group and overall. All collected data will be presented in listings which will be sorted by treatment, subject ID, and visit when it is appropriate. Summaries, data listings, and statistical analyses will be generated using SAS® Version 9.4 or higher.

#### 9.2 Analysis Populations

#### 9.2.3 Safety population

The safety population will include all randomized subjects who received at least one dose ofthe study drug. Analysis on the safety population will group subjects according to the treatment received.

## 9.3 Unit of Analysis

# 9.4 Definition of Study Day or Dosing Day

Study and dosing days are defined as follows:

Study Day = [Event date – Randomization date + 1] if after

randomization[Event date - Randomization date] if

before randomization

Dosing Day= [Event date – First dosing date + 1] if after first dosing

date [Event date – First dosing date] if before first

dosing date.

Note that with the definition above, days of "0" will not be used.

For subjects whose reference date is missing, the study day will also be categorized asmissing.

# 9.5 Missing and Partial Data

#### Adverse event onset

If onset date is completely missing, date is set to date of first dose.

If year is present and month and day are missing or year and day are present and month ismissing:

- o If year = year of first dose, then set month and day to month and day of first dose.
- o If year < year of first dose, then set month and day to December 31.
- o If year > year of first dose, then set month and day to January 1.

If month and year are present and day is missing:

- If year = year of first dose and
  - month = month of first dose, then set day to day of first dose date.
  - month < month of first dose, then set day to last day of month.
  - month > month of first dose, then set day to first day of month.
- o If year < year of first dose, then set day to last day of month.
- o If year > year of first dose, then set day to first day of month.

For all other cases, set date to date of first dose.

#### Adverse event end date

If year is present and month and day are missing or year and day are present and month ismissing, set end month and day to December 31.

If month and year are present and day is missing, set the day to last day of the month. If fatal event, date is set to minimum of imputed end date and death date. For all other cases, set date to missing.

For summaries that present distribution of time expressed in weeks and months, weeks willbe defined as days divided by 7 and months as days divided by 30.4375.

#### 9.6 Protocol Deviations

#### 9.7 Subjects Disposition

The number and percentage of subjects randomized and included in each analysis population will be summarized by treatment and overall. Reasons for excluding subjects from the analysis populations will be presented in a by-subject listing.

The number of randomized subjects who completed the study, discontinued early from studydrug, and reasons for discontinuation will be summarized by treatment group and overall.

The Case Report Form (CRF) lists the following reasons why subjects may discontinuetreatment before completing of the study:

- Non-Fatal Adverse Event
- Protocol Violation
- Lost to Follow Up
- Pregnancy
- Disease Progression
- Physician Decision
- Subject Non-Compliance
- Death
- Study Terminated by Sponsor
- Withdrawal by Subject
- Other

# 9.8 Demographics and Baseline Characteristics

Continuous variables will be summarized using the number of subjects (n), mean, SD, median, 25th and 75th percentiles, and minimum and maximum. Categorical variables will besummarized using counts and percentages. Summary data will be presented by treatment group and overall.

The following demographic will be summarized based on ITT population and Safetypopulation:

- Age
- Gender,
- Ethnicity
- Race

The following baseline ocular assessments will be summarized based on Safety population:

- Pain Visual Analog Scale (VAS)
- Best corrected distance visual acuity (BCDVA)
- Corneal Fluorescein Staining (prior to Schirmer's Test) Modified Oxford GradingScale
- Corneal Sensitivity Mean Score
- Schirmer's Test without Anesthesia

